## 7. SAFETY

### 7.1 SPECIFICATION OF SAFETY PARAMETERS

The Investigator is responsible for monitoring the safety of participants who have enrolled in the study. Safety assessments will be based on medical review of adverse events and the results of safety evaluations at specified time points as described in Section 6.9, Schedule of Events. Any clinically significant adverse events persisting at the end of treatment visit will be followed by the Investigator until resolution/stabilization or death, whichever comes first.

### 7.2 DEFINITIONS

#### 7.2.1 ADVERSE EVENT (AE)

An adverse event is defined as any undesirable physical, psychological or behavioral effect experienced by a participant before and during their participation in an investigational study, in conjunction with the use of the investigational product, whether or not considered intervention-related (21 CFR 312.32 (a)). In general, this includes signs or symptoms experienced by the participant from the time of signing the informed consent to completion of the study.

AEs may include, but are not limited to:

- Subjective or objective symptoms spontaneously offered by the participant and/or observed by the Investigator or medical staff.
- Clinically significant laboratory abnormalities.
- A significant worsening of the participant's condition from study entry.
- Disease signs and symptoms and/or laboratory abnormalities existing prior to the use of the study treatment that resolve but then recur after treatment.
- Disease signs and symptoms and/or laboratory abnormalities existing prior to the use of the study treatment which increase in frequency, intensity, or a change in quality after treatment.

#### 7.2.2 SERIOUS ADVERSE EVENT (SAE)

An AE or suspected adverse reaction is considered "serious" if, in the view of the Investigator, it results in any of the following outcomes:

- Death,
- A life-threatening adverse event,
- In-patient hospitalization or prolongation of existing hospitalization,
- A persistent or significant incapacity or substantial disruption of the ability to conduct normal life functions, or
- A congenital anomaly/birth defect.

Important medical events that may not result in death, be life-threatening, or require hospitalization may be considered serious when, based upon appropriate medical judgment, they may jeopardize the participant and/or participant may require medical or surgical intervention to prevent one of the outcomes listed in this definition. Examples of such medical events include:

- Allergic bronchospasm requiring intensive treatment in an emergency room or at home,
- Blood dyscrasias or convulsions that do not result in in-patient hospitalization, or
- The development of drug dependency or drug abuse.

### 7.2.3 UNANTICIPATED PROBLEMS (UP)

The Office for Human Research Protections (OHRP) considers UPs involving risks to participants or others to include, in general, any incident, experience, or outcome that meets all of the following criteria:

1. Unexpected in terms of nature, severity, or frequency given (a) the research procedures that are described in the protocol-related documents, such as the IRB-approved research protocol and informed consent document; and (b) the characteristics of the participant population being studied;
2. Related or possibly related to participation in the research (“possibly related” means there is a reasonable possibility that the incident, experience, or outcome may have been caused by the procedures involved in the research); and
3. Suggests that the research places participants or others at a greater risk of harm (including physical, psychological, economic, or social harm) than previously known or recognized.

This study will use the OHRP definition of UP.

### 7.2.4 SEVERITY OF EVENT

The Investigator will grade the severity of each AE using, when applicable, the current version of the [CTCAE v5.0](#). In the event of an AE for which no grading scale exists, the Investigator will classify the AE as defined below:

- **Grade 1** – Mild; asymptomatic or mild symptoms, or clinical or diagnostic observations only; intervention not indicated.
- **Grade 2** – Moderate; minimal, local or noninvasive intervention indicated, or limiting age-appropriate instrumental activities of daily living (ADL)
- **Grade 3** – Severe or medically significant but not immediately life-threatening, or hospitalization or prolongation of hospitalization indicated, or disabling, or limiting self-care ADL.
- **Grade 4** – Life-threatening consequences, or urgent intervention indicated.
- **Grade 5** – Death related to AE.

### 7.2.5 ASSESSMENT OF CAUSALITY RELATIONSHIP TO STUDY AGENT

For all collected AEs, the clinician who examines and evaluates the participant will determine the AE's causality based on temporal relationship and their clinical judgment. The degree of certainty about causality will be graded using the categories below.

- **Definite** – The AE is clearly related to the study treatment.
- **Possible** – The AE may be related to the study treatment.
- **Unrelated** –The AE is clearly NOT related to the study treatment.

### 7.3 EXPECTEDNESS

The Sponsor-investigator will be responsible for determining whether an AE is expected or unexpected. An AE will be considered unexpected if the nature, severity, or frequency of the event is not consistent with the risk information previously described for the study agent.

## 7.4 ADVERSE EVENT LIST

### 7.4.1 ADVERSE EVENT LIST FOR XISOMAB 3G3

Detailed information about the risks and expected AEs of xisomab 3G3 may be found in the current edition of the manufacturer's investigator brochure. In brief, 10 (48%) of 21 subjects experienced a total of 20 treatment emergent adverse events (TEAEs), of which 7 (44%) of 16 subjects received xisomab 3G3 and 3 (60%) of 5 subjects were exposed to placebo. A total of 3 (19%) subjects receiving xisomab 3G3 experienced 5 events that were suspected to be possibly treatment-related by the PI. The highest incidence of TEAEs by organ system was skin and subcutaneous tissue disorders, experienced by 3 (19%) xisomab 3G3-treated subjects and 1 (20%) placebo subject. The most common TEAE in this study was productive cough, experienced by 2 (13%) xisomab 3G3-treated subjects. All other TEAEs were experienced by 1 subject each. The majority of events (17) were mild (Grade 1) in severity and 3 were moderate (Grade 2). Moderate events included increased diastolic BP, productive cough, and upper respiratory tract infection.

## 7.5 ADVERSE EVENT ASSESSMENT AND FOLLOW-UP

The occurrence of an UP, AE or SAE may come to the attention of study personnel during study visits and interviews of a study participant presenting for medical care, or upon review by a study monitor. All AEs including local and systemic reactions not meeting the criteria for SAEs will be captured on the appropriate CRF, except for AEs definitely attributable to participant's planned anti-cancer treatment regimen. Information to be collected includes event description, time of onset, clinician's assessment of severity, seriousness, expectedness, relationship to study product (assessed only by those with the training and authority to make a diagnosis), and date of resolution/stabilization of the event. All AEs occurring while on study must be documented appropriately regardless of relationship. All AEs will be followed to adequate resolution.

Any medical condition that is present at the time that the participant is screened will be considered as baseline and not reported as an AE. However, if the study participant's condition deteriorates at any time during the study, it will be recorded as an AE.

Changes in the severity of an AE will be documented to allow an assessment of the duration of the event at each level of severity to be performed. AEs characterized as intermittent require documentation of onset and duration of each episode. At each study visit, the Investigator will inquire about the occurrence of AE/SAEs since the last visit. Events will be followed for outcome information until resolution or stabilization.

The Investigator will record all reportable events with start dates occurring any time after informed consent is obtained until 60 days post study agent dose or until the participant receives alternative anticoagulant therapy, whichever occurs first. Any SAE that occurs after treatment with alternative anticoagulant therapy will be reported only if the Investigator or current treating physician has assessed the SAE as related to the study treatment. Adverse events will be evaluated using the current version of the [CTCAE v5.0](#).

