Primary Objectives	To evaluate the antithrombotic efficacy of prophylactic xisomab 3G3 treatment in cancer patients with a central venous catheter.

Secondary Objectives	To determine the safety and tolerability of prophylactic xisomab 3G3 treatment as measured by the incidence and severity of adverse events in cancer patients with a central venous catheter.
Exploratory Objective	Assessment of participant coagulation profiles, and the incidence of line occlusion requiring medical interventions to obtain patency.
Primary Endpoints	The number of participants with catheter-associated thrombosis, as defined by the total incidence of symptomatic and asymptomatic thrombosis, and thrombotic occlusion leading to device failure (start: administration of xisomab; end: Day 18)
Secondary Endpoints	The number of subjects with treatment-related adverse events (TRAEs) and treatment-emergent adverse events (TEAEs) will be summarized using frequency counts (start: time of consent, end: Day 60)
Exploratory Endpoints	Quantification of coagulation parameters and assessment of catheter occlusion (start: pre-dose, end: Day 18 [i.e., post-dose]): 
 
a. Activated partial thromboplastin time (aPTT)
 
b. Pharmacokinetic (PK) evaluation
 
c. Time to symptomatic catheter-associated thrombosis
 
d. Proportion of participants with a catheter occlusion requiring medical intervention
 

Number of Participants	
Duration of Therapy	1 day
Duration of Follow Up	60 days [post catheter placement]
Key Inclusion Criteria	
 
• Men and women, aged <math>\geq</math> 18 years and members of all races and ethnic groups will be included.
 
• Participants with any solid tumor malignancy that will undergo insertion of a central venous catheter (PICC or indwelling subclavian vein central venous catheter) as part of planned cancer-directed therapy per institutional standards
 
• Able to wait 1 day post-study drug infusion before receiving cancer-directed therapy.
 
• ECOG performance status <math>\leq</math> 2
 
• Expected life expectancy of <math>>6</math> months
 
• At time of enrollment, must have adequate platelet count (<math>>100 \times 10^9/L</math>)
 

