## 2.2.2 SECONDARY OBJECTIVES AND ENDPOINTS

Objective	Endpoint	Start	End
To evaluate the safety and tolerability of xisomab 3G3 in cancer patients with a PICC or indwelling catheter	
 
1. Incidence of major and clinically-relevant bleeding [refer to Section 6.1.9.1]
 
2. Incidence of xisomab 3G3-associated toxicities [per CTCAE v5.0]
 
	Administration of xisomab 3G3 (Day 1 ± 2 days)	End of follow-up (Day 60)

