#### **6.1.9 ADVERSE EVENT EVALUATION**

Toxicities and adverse experiences will be assessed at each visit using the [CTCAE v5.0](#).

Safety will be monitored by assessing physical examination, vital signs, and weight, performance status, hematology, chemistry, coagulation, and pregnancy, as well as collecting of the AEs and medications at study visits.

Adverse events will be monitored from the time the participant signs the informed consent form, but will not be included for analysis if occurring before the study agent is given. Participants will be instructed to report all AEs during the study and will be assessed for the occurrence of AEs throughout the study. All AEs (serious and non-serious) must be recorded in the medical record and (e)CRFs regardless of the assumption of a causal relationship with the study drug; however, known AEs associated with a participant's planned anticancer treatment regimen will not be collected except for the development of grade 3-4 thrombocytopenia. For details on AE collection and reporting, refer to Section 7, Safety.

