#### 8.2.3 ANALYSIS OF THE SECONDARY ENDPOINTS

The incidence of major or clinically relevant non-major bleeding (defined in Section 6.1.9.1), along with 95% CI, will be assessed using the safety analysis set. The proportion of safety set participants with these bleeding events will also be separately estimated for each catheter type.

The incidence of xisomab 3G3-associated toxicities will be assessed using the safety analysis set. Descriptive statistics of safety will be presented using CTCAE v5.0. All on-study AEs (from time of consent), treatment-related AEx (from time of xisomab infusion), SAEs, and treatment-related SAEs will be tabulated using worst grade per NCI CTCAE v5.0 criteria by system organ class and preferred term. On-study abnormal lab parameters including hematology, chemistry, liver function, and renal function will be summarized using worst grade NCI CTCAE v5.0 criteria.

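### Two conflicting rules for leaving out adverse events linked to the cancer regimen leave non-serious bleeding, skin and delayed allergic events open to going uncollected, and neither rule can deliver the planned safety tables

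*Combined protocol and SAP*

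**What the plan says.** Section 6.1.9 starts from full collection: "All AEs (serious and non-serious) must be recorded in the medical record and (e)CRFs regardless of the assumption of a causal relationship". The relationship meant there is to xisomab. It then carves out a class of event: "known AEs associated with a participant's planned anticancer treatment regimen will not be collected except for the development of grade 3-4 thrombocytopenia".

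Section 7.5 has a different carve-out. AEs go on the case report form (CRF) "except for AEs definitely attributable to participant's planned anti-cancer treatment regimen", and thrombocytopenia gets no special treatment. The same paragraph adds: "All AEs occurring while on study must be documented appropriately regardless of relationship".

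The endpoints and analyses carry no such filter. The synopsis endpoint reads: "The number of subjects with treatment-related adverse events (TRAEs) and treatment-emergent adverse events (TEAEs) will be summarized using frequency counts". Section 2.2.2 lists "Incidence of major and clinically-relevant bleeding" and xisomab-associated toxicities. Section 8.2.3 tabulates "All on-study AEs (from time of consent" onward) and reports bleeding incidence with a 95% CI in the safety set.

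On causality, Section 7.2.5 says: "The degree of certainty about causality will be graded using the categories below". Those categories (definite, possible, unrelated) refer to the study treatment only, and they are applied to AEs that have been collected.

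**The concern.** The two carve-outs ask different questions. Section 6.1.9, read literally, asks whether the type of event is known for the regimen. Section 7.5 asks whether this particular event was certainly caused by the regimen. Site staff cannot follow both, and no reference list defines what is known and no scale defines certainty about the regimen.

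What is at stake is the completeness of the secondary safety endpoint. Section 1.4.1 describes the safety profile as still being established, raises a possible effect on hemostasis, and lists acute and delayed allergic reactions as possible. Cancer regimens can produce the same kinds of event. An event filtered out before collection is never graded for its relation to xisomab, and with no control arm nothing in the data would show that events are missing.

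**Working it through.** The documents give no AE or bleeding rate for this population, so the check is mainly a comparison of texts.

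**1. The two rules side by side.** Treatment of an AE under a literal reading of each section:

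| AE | 6.1.9 (type of event) | 7.5 (individual cause) | Needed for the TEAE count and the 8.2.3 table |
|---|---|---|---|
| Known for the regimen, regimen certainly the cause | left out | left out | yes |
| Known for the regimen, cause unclear | left out | captured | yes |
| Not known for the regimen, but judged certainly due to it | captured | left out | yes |
| Grade 3-4 thrombocytopenia, certainly due to the regimen | captured | left out | yes |

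The sections disagree in three of the four rows. The second row matters most, because it holds events that may be due to xisomab. In every row at least one rule leaves out an AE that the planned count and table need.

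**2. The statements about recording everything.** The clause in 6.1.9 concerns relation to the study drug, so it does not by itself contradict a carve-out for the regimen. The sentence in 7.5 names no agent and sits in the same paragraph as the exception, so that conflict is internal to 7.5.

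**3. What other sections protect.**
- Footnote F of the Schedule of Events (6.9) asks for grade 3-4 SAEs, related or not, up to 60 days after catheter placement. This covers most serious major bleeds.
- Footnote F also places bleeding assessment inside the AE evaluation. That shows intent to assess all of it, but does not exempt bleeding from 6.1.9 or 7.5.
- Section 5.3.4 treats allergic and infusion reactions as xisomab-related, with onset typically within hours. Section 5.1 does not allow cancer therapy until 2 days after study drug, so a typical acute reaction comes before the regimen. (The inclusion criteria speak of a 1-day interval. The passages need reconciling, but a reaction within hours precedes either.)

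What remains exposed is mainly non-serious: clinically relevant non-major or lower-grade bleeding, skin reactions, and delayed allergic reactions.

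**4. Overlap.** Take the 60 days after dosing in 7.5, and assume that therapy starts at the earliest time and that collection does not stop early for another anticoagulant. Then 60 - 2 = 58 of 60 days (97%) can overlap with the regimen.

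**5. Illustration only.** The denominator is the planned 50. That figure reproduces from 8.3.1 by the normal approximation: n = [(1.960 x sqrt(0.6 x 0.4) + 0.842 x sqrt(0.4 x 0.6)) / 0.20]^2 = 47.09, rounded up to 48, and 48 / 0.96 = 50. Suppose that 5 participants have a qualifying bleed and 0 to 3 of them go uncollected. Both counts are assumptions. Section 8.2.3 names no interval method, so Clopper-Pearson is used:

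| Recorded | Rate | 95% CI |
|---|---|---|
| 5/50 | 10% | 3.3% to 21.8% |
| 4/50 | 8% | 2.2% to 19.2% |
| 3/50 | 6% | 1.3% to 16.5% |
| 2/50 | 4% | 0.5% to 13.7% |

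The intervals overlap heavily. The table shows how sensitive a small count is, not how many events would be lost.

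**The case against.** The best defence is that bleeding is a named endpoint. Section 6.1.9.1 defines it with no causal condition, footnote F requires its assessment, and 8.2.3 analyses it without an attribution filter. A careful site would not let a general AE rule override that. The wording in 6.1.9 can also be read as events attributed to the regimen, which comes close to 7.5. Under 7.5 the endpoint of xisomab-associated toxicities loses little, since an event certainly due to the regimen is not xisomab-associated. Section 3.2 excludes regimens with a 15% or higher incidence of grade 3-4 thrombocytopenia within 14 days of study drug, and transfusions before the end-of-treatment visit are recorded.

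Much of this stands, and it rules out three stronger readings. A reader might infer that bleeds and hypersensitivity reactions shared with the regimen would never be recorded. The safeguards above do not support that for serious bleeds or acute reactions. A reader might infer that lost events could not be recovered. Section 6.1.9 also requires entry in the medical record, 6.7 allows chart review at Day 60, and bleeding that prompts medical attention would be expected to leave a source record. Even so, the plan provides for no such retrieval. A reader might also infer a demonstrated downward bias. The documents support only a possible one. Phase 1 does not settle it either: skin events occurred in 3 of 16 on xisomab (19%) and 1 of 5 on placebo (20%).

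The defence does not remove the conflict. No section exempts non-serious bleeding, skin or delayed allergic events, and the treatment-emergent count and the 8.2.3 table cannot be complete under either rule.

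**Conclusion.** The point holds as an inconsistency in data collection that bears on a stated endpoint. Sections 6.1.9 and 7.5 differ in their test and in the thrombocytopenia exception. Both conflict with the synopsis count and the 8.2.3 table, and 7.5 conflicts with itself. Under the literal reading of 6.1.9, non-serious events shared with the regimen could go uncollected, which could bias the safety rates downward. The size is unknown, because the documents give no event rate and no indication of how staff would apply the rule. The conclusion rests on that literal reading and on regimens whose known effects include bleeding, skin or delayed allergic events. The primary endpoint, sample size and power are unaffected. It should be fixed, but it does not undermine the trial.

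**What to change.** Put one collection rule in 6.1.9 and 7.5, and keep the existing window from consent.

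- **At minimum:** state that all bleeding under 6.1.9.1, and any AE possibly related to xisomab, is always recorded in the CRF, whatever the regimen is known to cause.
- **Preferably:** record all AEs, with one field for relation to xisomab and another for relation to the regimen, and separate them at analysis.
- **If any carve-out stays:** define it once, and relabel the treatment-emergent count and the 8.2.3 table to say which events are left out.

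The cost is a wording amendment, one added CRF field under the preferred option, and modest extra AE entry for 50 participants. No visits are added.

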## 7.6 REPORTING PROCEDURES

#### 7.6.1 OHSU IRB REPORTING OF UNANTICIPATED PROBLEMS AND ADVERSE EVENTS

Unanticipated Problems and AEs will be reported to OHSU IRB according to the policies, procedures and guidelines posted on the [OHSU IRB web site](#).

Per regulatory requirements, if an event is assessed by the Sponsor Institution as a Serious Unexpected Adverse Reaction (SUSAR), it is the responsibility of the Sponsor Institution to submit the SUSAR to Regulatory Authorities according to applicable regulations. In addition, the SUSAR will be distributed to the Investigators/sites utilizing a Council for International Organizations of Medical Sciences (CIOMS) report form, or the MedWatch 3500A form). The Investigator/site will submit a copy of the report to their respective IRB or IEC per the governing institutional requirements and in compliance with local laws and guidelines.

Events that must be reported by the Investigator to the IRB are detailed in the OHSU IRB **Investigator Guidance: Prompt Reporting Requirements (HRP-801)**. At a minimum, events requiring reporting to the IRB include:

- Any new or increased risk related to the research, including AEs or IND safety reports that require a change to the protocol or consent,
- New FDA black box warning,
- Publications identifying new risks,
- Data Safety Monitoring Board/Committee letters recommending changes or discussing new risks
- Unanticipated adverse device effect
- Unauthorized disclosure of confidential participant information

#### 7.6.2 MEDWATCH REPORTING

The Sponsor is required to report AEs to the FDA through the MedWatch reporting program, even if the trial involves a commercially available agent. Adverse events to be reported include any UPs (i.e., not listed in the package insert) and any SAEs with a suspected association to the investigational product.

Adverse events that occur during clinical studies are to be reported to FDA as specified in the investigational new drug/biologic regulations using Form FDA 3500, the MedWatch Voluntary Reporting form (available [here](#)), or completed [online](#). A copy of Form FDA 3500 and supporting materials will be kept on file in the study regulatory binder.

